6.6 Rescue Medications & Supportive Care

6.6.1 Supportive Care Guidelines

Subjects should receive appropriate supportive care measures as deemed necessary by the treating investigator. Suggested supportive care measures for the management of adverse events with potential immunologic etiology are outlined in Section 6.2. Where appropriate, these guidelines include the use of oral or intravenous treatment with corticosteroids as well as additional anti-inflammatory agents if symptoms do not improve with administration of corticosteroids. Note that several courses of steroid tapering may be necessary as symptoms may worsen when the steroid dose is decreased. For each disorder, attempts should be made to rule out other causes such as metastatic disease or bacterial or viral infection, which might require additional supportive care. The treatment guidelines are intended to be applied when the investigator determines the events to be related to nivolumab.

Note: if after the evaluation the event is determined not to be related, the investigator does not need to follow the treatment guidance (as outlined below). Refer to Section 6.2 for dose modification.

It may be necessary to perform conditional procedures such as bronchoscopy, endoscopy, or skin photography as part of evaluation of the event.

6.6.2 Management of Infusion Reactions: Signs and symptoms usually develop during or shortly after drug infusion and generally resolve completely within 24 hours of completion of infusion

Table 4 Infusion Reaction Treatment Guidelines

| NCI CTCAE Grade | Treatment | Premedication at subsequent dosing |
|---|--|--|
| Grade 1 Mild reaction; infusion interruption not indicated; intervention not indicated | Increase monitoring of vital signs as medically indicated until the subject is deemed medically stable in the opinion of the investigator. | None |
| Grade 2 Requires infusion interruption but responds promptly to symptomatic treatment (e.g., antihistamines, NSAIDS, narcotics, IV fluids); prophylactic medications indicated for <=24 hrs | Stop Infusion and monitor symptoms. Additional appropriate medical therapy may include but is not limited to: IV fluids Antihistamines NSAIDS Acetaminophen Narcotics | Subject may be premedicated at least 30 minutes prior to infusion of nivolumab with: Diphenhydramine 50 mg po (or equivalent dose of antihistamine). Acetaminophen 500-1000 mg po (or equivalent dose of antipyretic). |

| NCI CTCAE Grade | Treatment | Premedication at subsequent dosing |
|---|---|------------------------------------|
| | 
Increase monitoring of vital signs as medically indicated until the subject is deemed medically stable in the opinion of the investigator. If symptoms resolve within one hour of stopping drug infusion, the infusion may be restarted at 50% of the original infusion rate (e.g., from 100 mL/hr to 50 mL/hr), if no further complications ensue after 30 minutes, the rate may be increased to 100% of the original infusion rate. Monitor the subject closely. If symptoms recur, then no further study medication will be administered at that visit. Otherwise dosing will be held until symptoms resolve and the subject should be premedicated for the next scheduled dose.
 
Subjects who develop Grade 2 toxicity despite adequate premedication should be permanently discontinued from further trial treatment administration.
 | |
| Grades 3 or 4 Grade 3: Prolonged (i.e., not rapidly responsive to symptomatic medication and/or brief interruption of infusion); recurrence of symptoms following initial improvement; hospitalization indicated for other clinical sequelae (e.g., renal impairment, pulmonary infiltrates) Grade 4: Life-threatening; pressor or ventilatory support indicated | 
Stop Infusion. Additional appropriate medical therapy may include but is not limited to:
 
 IV fluids Antihistamines NSAIDS Acetaminophen Narcotics Oxygen Pressors Corticosteroids Epinephrine 
Increase monitoring of vital signs as medically indicated until the subject is deemed medically stable in the opinion of the investigator. Hospitalization may be indicated. Subject is permanently discontinued from further trial treatment administration.
 | No subsequent dosing |
| Appropriate resuscitation equipment should be available in the room and a physician readily available during the period of drug administration. | | |

6.7 Diet/Activity/Other Considerations

6.7.1 Diet

Subjects should maintain a normal diet unless modifications are required to manage an AE such as diarrhea, nausea or vomiting. Seville orange, star fruit, grapefruit and their juices affect P450 and PgP activity and concomitant use with nivolumab and metformin combination should be avoided.

6.7.2 Contraception

Nivolumab and Metformin may have adverse effects on a fetus in utero. Furthermore, it is not known if nivolumab and metformin have transient adverse effects on the composition of sperm. For this trial, male subjects will be considered to be of non-reproductive potential if they have azoospermia (whether due to having had a vasectomy or due to an underlying medical condition).

Female subjects will be considered of non-reproductive potential if they are either:

- (1) postmenopausal (defined as at least 12 months with no menses without an alternative medical cause; in women < 45 years of age a high follicle

stimulating hormone (FSH) level in the postmenopausal range may be used to confirm a post-menopausal state in

women not using hormonal contraception or hormonal replacement therapy. In the absence of 12 months of amenorrhea, a single FSH measurement is insufficient.);

OR

(2) have had a hysterectomy and/or bilateral oophorectomy, bilateral salpingectomy or bilateral tubal ligation/occlusion, at least 6 weeks prior to screening;

OR

(3) has a congenital or acquired condition that prevents childbearing.

Female and male subjects of reproductive potential must agree to avoid becoming pregnant or impregnating a partner, respectively, while receiving study drug and for 120 days after the last dose of study drug by complying with one of the following:

(1) practice abstinence[†] from heterosexual activity;

OR

(2) use (or have their partner use) acceptable contraception during heterosexual activity.

Acceptable methods of contraception are[‡]:

Single method (one of the following is acceptable):

- intrauterine device (IUD)
- vasectomy of a female subject's male partner
- contraceptive rod implanted into the skin

Combination method (requires use of two of the following):

- diaphragm with spermicide (cannot be used in conjunction with cervical cap/spermicide)
- cervical cap with spermicide (nulliparous women only)
- contraceptive sponge (nulliparous women only)
- male condom or female condom (cannot be used together)
- hormonal contraceptive: oral contraceptive pill (estrogen/progestin pill or progestin-only pill), contraceptive skin patch, vaginal contraceptive ring, or subcutaneous contraceptive injection

[†]Abstinence (relative to heterosexual activity) can be used as the sole method of contraception if it is consistently employed as the subject's preferred and usual lifestyle and if considered acceptable by local regulatory agencies and ERCs/IRBs. Periodic abstinence (e.g., calendar, ovulation, sympto-thermal, post-ovulation methods, etc.) and withdrawal are not acceptable methods of contraception.

[‡]If a contraceptive method listed above is restricted by local regulations/guidelines, then it does not qualify as an acceptable method of contraception for subjects participating at sites in this country/region.

Subjects should be informed that taking the study medication may involve unknown risks to the fetus (unborn baby) if pregnancy were to occur during the study. In order to participate in

the study subjects of childbearing potential must adhere to the contraception requirement (described above) from the day of study medication initiation (or 14 days prior to the initiation of study medication for oral contraception) throughout the study period up to 120 days after the last dose of trial therapy. If there is any question that a subject of childbearing potential will not reliably comply with the requirements for contraception, that subject should not be entered into the study.

6.7.3 Use in Pregnancy

If a subject inadvertently becomes pregnant while on treatment with Nivolumab and Metformin, the subject will immediately be removed from the study. The site will contact the subject at least monthly and document the subject's status until the pregnancy has been completed or terminated. The outcome of the pregnancy will be reported to BMS without delay and within 24 hours to BMS and within 2 working days to Sponsor if the outcome is a serious adverse experience (e.g., death, abortion, congenital anomaly, or other disabling or life-threatening complication to the mother or newborn).

The study investigator will make every effort to obtain permission to follow the outcome of the pregnancy and report the condition of the fetus or newborn to the Sponsor. If a male subject impregnates his female partner the study personnel at the site must be informed immediately and the pregnancy reported to Sponsor as described above and in Section 8.2.4.

6.7.4 Use in Nursing Women

It is unknown whether Nivolumab is excreted in human milk. Since many drugs are excreted in human milk, and because of the potential for serious adverse reactions in the nursing infant, subjects who are breast-feeding are not eligible for enrollment. Patients should be advised not breastfeed while on Nivolumab and Metformin or for at least 3 months after discontinuation.

6.8 Duration of Therapy

In the absence of treatment delays due to adverse event(s), treatment may continue for *2 years* or until one of the following criteria applies:

- Disease progression,
- Intercurrent illness that prevents further administration of treatment,
- Unacceptable adverse event(s),
- Patient decides to withdraw from the study, or
- General or specific changes in the patient's condition render the patient unacceptable for further treatment in the judgment of the investigator.

6.9 Duration of Follow Up

Patients will be followed as outlined in study calendar in section 7 after removal from study or until death, whichever occurs first. Patients removed from study for unacceptable adverse event(s) will be followed until resolution or stabilization of the adverse event.

6.10 Criteria for Removal from Study

Patients will be removed from study when any of the criteria listed in Section 5.4 applies. The reason for study removal and the date the patient was removed must be documented in the Case Report Form.

6.11 Discontinuation of Study Therapy after CR

Discontinuation of treatment may be considered for subjects who have attained a confirmed CR that have been treated for at least 24 weeks with nivolumab and metformin and had at least two treatments with nivolumab and metformin beyond the date when the initial CR was declared. Subjects who then experience radiographic disease progression may be eligible for additional treatment with nivolumab and metformin via the Second Course Phase at the discretion of the investigator as detailed in Section 8.1.7.2.

6.12 Subject Replacement Strategy

Patients who do not complete the intended course of therapy due to reasons other than toxicity, clinical or radiographic disease progression will be considered as in-evaluable for the primary endpoint and will be replaced. Subject are not able to tolerate metformin despite 2 dose reductions in the first 2 weeks of the trial (Metformin only phase) will be considered inevaluable and replaced.

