8.1.1.6 Trial Compliance (Medication/Diet/Activity/Other)

Compliance with Metformin will be determined using drug diary and pill counts performed on day 1 of each cycle. Patients who take less than 80% of their prescribed dose of nivolumab and/or metformin in the first 2 cycles due to reasons other than toxicity, clinical or radiographic disease progression will be considered inevaluable for the primary endpoint and will be replaced.

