10.3 Evaluation of Response

All patients included in the study must be assessed for response to treatment, even if there are major protocol treatment deviations or if they are ineligible. Each patient will be assigned one of the following categories: 1) complete response, 2) partial response, 3) stable disease, 4) progressive disease, 5) early death from malignant disease, 6) early death from toxicity, 7) early death because of other cause, or 9) unknown (not assessable, insufficient data). [Note: By arbitrary convention, category 9 usually designates the "unknown" status of any type of data in a clinical database.]

All of the patients who met the eligibility criteria (with the possible exception of those who received no study medication) should be included in the main analysis of the response rate. Patients in response categories 4-9 should be considered to have a treatment failure (disease progression). Thus, an incorrect treatment schedule or drug administration does not result in

exclusion from the analysis of the response rate. Precise definitions for categories 4-9 will be protocol specific.

All conclusions should be based on all eligible patients. Subanalyses may then be performed on the basis of a subset of patients, excluding those for whom major protocol deviations have been identified (e.g., early death due to other reasons, early discontinuation of treatment, major protocol violations, etc.). However, these subanalyses may not serve as the basis for drawing conclusions concerning treatment efficacy, and the reasons for excluding patients from the analysis should be clearly reported. The 95% confidence intervals should also be provided.

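### Sections 6.12 and 8.1.1.6 remove and replace some treated patients for the primary endpoint, 10.3 and 10.4 keep them, and no passage says which set the 18/28/3 rule uses

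*Combined protocol and SAP*

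**What the plan says.** **Sections that remove patients.** Section 6.12 covers those that "do not complete the intended course of therapy due to reasons other than toxicity, clinical or radiographic disease progression will be considered as in-evaluable"; this status concerns the primary endpoint, and these patients are replaced. Its second sentence ("Subject are not able to tolerate metformin despite 2 dose reductions in the first 2 weeks of the trial") makes metformin intolerance in the lead-in a further ground for being inevaluable and replaced. Section 8.1.1.6 covers patients who took under 80% of the prescribed nivolumab and/or metformin in the first two cycles, again for reasons other than toxicity or progression; they "will be considered inevaluable for the primary endpoint and will be replaced".

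**Sections that keep patients.** Section 10.3 puts into the main response-rate analysis "All of the patients who met the eligibility criteria (with the possible exception of those who received no study medication"). It adds that "an incorrect treatment schedule or drug administration does not result in" exclusion from that analysis. It also says "Patients in response categories 4-9 should be considered to have a treatment failure (disease progression"); category 9 is unknown or not assessable. It then states "All conclusions should be based on all eligible patients". Subanalyses that leave patients out are allowed, but "these subanalyses may not serve as the basis for drawing conclusions concerning treatment efficacy". Section 10.4 includes in the efficacy evaluation every subject given any amount of study drug.

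**Sections that are silent.** The 18/28/3 rule in 10.1 and in the synopsis refers only to patients. The ORR in 10.2 is divided by total patients, undefined. Section 8.1.3.1 and note h of the study calendar replace patients who refuse biopsy #2 but do not give their ORR status.

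**The concern.** The same treated patient is outside the primary endpoint under one part of the protocol and inside it under another, and no passage gives either part precedence. The rule needs one response in 18 to continue and three in 28 to be positive, so one patient's status can decide either step. The trial is open label. If the set is settled after responses are known, the choice is driven by the data. If non-responders are replaced more often than responders, the reported ORR and the chance of a false positive both rise.

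**Working it through.** **Inputs.** From 10.1: 18 patients in stage 1, continue on 1 response (read as at least 1); 28 in total, positive on 3 or more; target ORR 15%, power 80%, alpha 0.1. The historical ORR is given only as below 5%, so I use 3% and 4%. The documents give no replacement rate; 10% and 20% are assumptions.

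**1. The plan's own design.** P(positive) = sum over x = 1 to 18 of Bin(x; 18, p) × P(Bin(10, p) ≥ max(0, 3 − x)).

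- p = 0.15: 0.803, matching the stated 80%.
- p = 0.04: 0.097, within alpha 0.1.
- p = 0.03: 0.049.

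**2. The sections side by side**, for eligible patients who received study drug:

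| Patient | 6.12 / 8.1.1.6 | 10.3 | 10.4 |
|---|---|---|---|
| Took 70% of metformin in cycles 1-2 for a non-medical reason, partial response documented | Out, replaced | In, responder | In |
| Same, never assessed | Out, replaced | In, failure (category 9) | In |
| Left for toxicity or progression after the lead-in | In | In | In |
| Could not tolerate metformin in the lead-in | Out, replaced | In | In (6.2.1 calls metformin a study drug) |
| Refused biopsy #2 | Replaced under 8.1.3.1 and note h; ORR status not stated | In | In |

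Sections 10.3 (eligible) and 10.4 (any drug, no eligibility condition) also differ from each other.

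**3. P(positive) in the evaluable set.** Let a fraction qn of non-responders and qr of responders be replaced. The response rate among evaluable patients is e = p(1 − qr) / [p(1 − qr) + (1 − p)(1 − qn)].

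- Equal rates (qr = qn): e = p, so nothing changes.
- Worst case (qr = 0), p = 0.04: 0.04/(0.04 + 0.96 × 0.90) = 0.0442, giving 0.122; with qn = 0.20, e = 0.0495, giving 0.155.
- Worst case, p = 0.03: e = 0.0332 and 0.0372, giving 0.063 and 0.082.
- Responders leaving at half the rate (qr = qn/2): 0.109 and 0.125 at 4%; 0.056 and 0.065 at 3%.

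**4. Opposite decisions, leaving unrelated to response.** The first 28 evaluable patients are compared with three other readings.

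(a) *First 28 treated, every replaced patient unassessable and so a failure.* The effective rate is p(1 − q). At ORR 15%: q = 0.10 gives 0.135 and P(positive) 0.738; q = 0.20 gives 0.12 and 0.659. Responders counted here are a subset of those in the evaluable set, so disagreement is only evaluable-positive/treated-negative: 0.803 − 0.738 = 0.065 and 0.803 − 0.659 = 0.145 (by unrounded values). At ORR 4% it is 0.021 and 0.040.

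(b) *First 28 treated, replaced patients assessed and their responses counted, as 10.3 requires.* By simulation at ORR 15%, disagreement is about 0.039 in each direction at 10% leaving and 0.063 to 0.064 in each direction at 20%. P(positive) in the first 28 treated stays about 0.80. At ORR 4% it is about 0.018 and 0.032 in each direction.

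(c) *All treated patients (28 + m) against the same cutoff of 3, with responses counted and the stage 1 look also counting all treated to that point.* Disagreement runs only evaluable-negative/treated-positive: about 0.05 at ORR 15% with 10% leaving. P(positive) at ORR 4% rises to about 0.12. With m = 3 and stage 1 held at 18, the exact values are 0.119 at 4% and 0.848 at 15%.

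**5. The reported estimate.** About 28/0.90 = 31 or 28/0.80 = 35 treated patients are needed for 28 evaluable. With three responders, and replaced patients counted as non-responders, the Clopper-Pearson results are 3/28 = 10.7% (2.3 to 28.2), 3/31 = 9.7% (2.0 to 25.8) and 3/35 = 8.6% (1.8 to 23.1).

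**The case against.** The best defence is that 18 and 28 are slots to be filled with evaluable patients: replacing someone for the primary endpoint makes most sense on that reading, and 10.3 and 10.4 would then govern only what is reported. Replacing patients who never get past a metformin-only lead-in is also a defensible choice, and leavers for toxicity or progression after the lead-in are kept, which limits bias. Much of this stands. The contradiction requires one governing rule; it does not by itself require replacement to be abandoned or confined to the biopsy cohort. But no passage says that 18 and 28 are evaluable slots, and 10.3 expressly bars conclusions from subsets that exclude patients.

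Three stronger readings are tempting and are not supported:

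- *The replacement rules necessarily inflate the false-positive rate.* If leaving is unrelated to response there is no change, and at ORR 3% even the worst case (0.082) stays below 0.1.
- *The evaluable set can only err towards a positive result.* That holds only if every replaced patient is unassessable. The triggers are non-completion and low dosing. The first scan comes at the end of cycle 2 and 6.8 allows two years of treatment, so some leavers may have been assessed, and under 10.3 a documented response counts.
- *Following 10.3 and 10.4 must cost power.* The fall to 0.738 or 0.659 belongs to the same extreme; if all leavers are assessed, power stays about 0.80.

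**Conclusion.** The contradiction holds and must be resolved before the primary analysis. It follows from the text alone and does not depend on any assumed rate. Its numerical effect does. At ORR 15% with 10% to 20% leaving regardless of response, the evaluable set and the first 28 treated give opposite decisions in 0.065 to 0.145 of trials, all one way, if no leaver is assessable. If all are assessed the figure is about 0.039 to 0.063 in each direction; a real trial could lie between these extremes. P(positive) at a true ORR of 4% exceeds 0.1 in the evaluable set only if non-responders are replaced more often than responders, reaching 0.122 to 0.155 in the worst case. The documents settle neither the leaving rate nor its relation to response, so none of these figures is a forecast.

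**What to change.** 1. State one governing primary ORR set in Section 10. The set consistent with 10.3 and 10.4 is eligible subjects who received any study drug, with documented responses counted whatever the dosing compliance and unassessable patients counted as non-responders. The sponsor should say whether subjects who received only lead-in metformin belong to it.
2. Delete the statement in 6.12 and 8.1.1.6 that patients are inevaluable for the primary endpoint. If lead-in-only subjects are kept, delete the matching word in the lead-in sentence of 6.12 as well.
3. In 10.1 and the synopsis, apply the rule to the first 18 and first 28 subjects of that set in order of enrolment. In 10.2, define total patients as the same set.
4. State that subjects who refuse biopsy #2 stay in the set. Subjects enrolled beyond the 28th as replacements are reported in the overall ORR and its confidence interval but do not enter the 18/28/3 decision. Section 10.3 needs a sentence to this effect, since it bases all conclusions on all eligible patients.
5. Report the evaluable-only ORR as a labelled sensitivity analysis. If responses are already known, report the 18/28/3 decision for both sets.

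The cost is wording, plus two consequences. The reported ORR may be slightly lower. The stated 80% power should be restated for the expected unassessable fraction: 0.803 if none, 0.738 at 10%, 0.659 at 20%.

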7. STUDY CALENDAR

Winship Protocol #: Winship4494-18
Protocol: Nivolumab + Metformin
Protocol/Amendment No.: Version 6/June 13, 2023
Study Flow Chart

36

| Trial Period: | | Treatment Cycles ^a | | | | | | | | | | End of Treatment | Post-Treatment | | |
|---|----------------|--------------------------------|-----|----------------|------|-----|-----|-----|-----|-----|-----|-------------------|---------------------|-------------------------------|--------------------|
| | | Main Study Screening (Visit 2) | | 1 ^a | 2 | 3 | 4 | 5 | 6 | 7 | 8 | | | | |
| Treatment Cycle/Title: | Day | D-14 | D-7 | D1 | D15 | | | | | | | Discon | Safety Follow-up | Follow Up Visits ^b | Survival Follow-Up |
| Scheduling Window (Days): | -28 to -1 | | | ± 3 | ± 3* | ± 3 | ± 3 | ± 3 | ± 3 | ± 3 | ± 3 | At time of Discon | 30 days post discon | Every 8 weeks post discon | Every 12 weeks |
| Informed Consent | X | | | | | | | | | | | | | | |
| Inclusion/Exclusion Criteria | X | | | | | | | | | | | | | | |
| Demographics and Medical History | X | | | | | | | | | | | | | | |
| Prior and Concomitant Medication Review | X | X | X | X | X | X | X | X | X | X | X | X | X | X | |
| Metformin Administration ^c | | X | X | X | X | X | X | X | X | X | X | | | | |
| Drug Diary and Pill Count (Metformin) section 13.5 ^c | | X | | X | X | X | X | X | X | X | X | X | | | |
| Blood glucose log for diabetic patients | | X | X | X | X | | | | | | | | | | |
| Nivolumab administration ^c | | | | X | | X | X | X | X | X | X | | | | |
| Post-study anticancer therapy status | | | | | | | | | | | | | X | X | |
| Survival Status | | | | | | | | | | | | | X | X | X |
| Review Adverse Events | | | X | X | X | X | X | X | X | X | X | X | X | X | |
| Full Physical Examination | X | X | | X | | X | X | X | X | X | X | | | | |
| Directed Physical Examination | | | | | X | | | | | | | | X | X | X |
| Vital Signs and Weight | X | X | | X | X | X | X | X | X | X | X | X | X | X | |
| ECOG Performance Status ^d | X ^d | X | | X | X | X | X | X | X | X | X | X | X | X | |
| Pregnancy Test – Urine or Serum β-HCG | X ^j | | | | | | | | | | | | | | |
| PT/INR and aPTT | X | | | | | | | | | | | | | | |
| CBC with Differential | X | X ^e | | X | X | X | X | X | X | X | X | X | X | X | |
| Comprehensive Serum Chemistry Panel | X | X ^e | | X | X | X | X | X | X | X | X | X | X | X | |
| Fasting triglyceride, cholesterol and glucose | X | | | | | X | | | X | | | | | | |
| CEA | | X | | X | X | | X | | X | | X | | | | |
| Urinalysis | X | | | | | X | | | X | | | X | | | |
| T3, FT4 and TSH | X | | | | X | | | X | | | X | X | X | X | |
| ECG | X | | | | | | | | | | | | | | |

| Trial Period: | Main Study Screening (Visit 2) | Treatment Cycles ^a | | | | | | | | | | End of Treatment | Post-Treatment | | |
|---|--------------------------------|-------------------------------|-----|----------------|----------------|----------------|----------------|----------------|---------|----------------|--------------------------------|---------------------|---------------------------|-------------------------------|--------------------|
| | | 1 ^a | | 2 | 3 | 4 | 5 | 6 | 7 | 8 | To be repeated beyond 8 cycles | | Safety Follow-up | Follow Up Visits ^b | Survival Follow-Up |
| Treatment Cycle/Title: | 1 ^a | D-14 | D-7 | D1 | D15 | | | | | | | Discon | | | |
| Day | | | | | | | | | | | | | | | |
| Scheduling Window (Days): | -28 to -1 | | | ± 3 | $\pm 3^*$ | ± 3 | ± 3 | ± 3 | ± 3 | ± 3 | At time of Discon | 30 days post discon | Every 8 weeks post discon | Every 12 weeks | |
| Tumor Imaging | X | | | | | X ^g | | X ^g | | X ^g | | | | | |
| Newly Obtained Tissue Collection ^h | X | | | X ^h | X ^h | | | | | | | | | | |
| Correlative Studies Blood Collection ⁱ | X | | | X ⁱ | X ⁱ | | X ⁱ | | | | | X ⁱ | | | |

- a. Each cycle is 4 weeks, and there is 14 days lead in period in cycle 1
- b. Only for patients with ongoing treatment related toxicities
- c. Metformin will be taken 500 mg po BID for D-14 to-12, 500 mg am and 1000 mg pm for D-11 to 8, 1000 mg am and 1000 mg pm for D- 7 to -1, and continued 1000 mg BID for the rest of the study (if not able to tolerate 1000 mg BID during D1-14 period subject will be on maximum tolerated dose). Study coordinator will call the patient on Day -13 to confirm the subject is taking the right dose of medication. Nivolumab will be given after biopsy#2 (same day or up to 5 days later), and then repeated every 4 weeks.
- d. ECOG performance status should be done within 14 days or less from day 1 of cycle 1
- e. Lab results from screening may be used if completed within 1 week of day -1
- f. Baseline imaging within 4 weeks of day 1 is acceptable
- g. Scans will be done at the end of cycle 2 (± 3 days), then repeated every 2 cycles (q 8 weeks)
- h. Paired biopsies (biopsy#1) will be obtained at baseline from all 28 patients within 28 days before Cycle 1 day 1 after consent is signed, subject #1-9, 19-23 (14 patients in total) will get post treatment biopsy (biopsy#2) cycle 1 Day 1 (same day or up to 5 days later) nivolumab will be given after biopsy#2 (same day or up to 5 days later) and subject# 10-18, 24-28 (14 patients in total) will get post treatment biopsy (biopsy#2) C1 Day 15 (same day or up to 5 days later). Most accessible metastatic disease tumor site will be biopsied by Emory Interventional Radiology. Same site will be biopsied at biopsy#1 and biopsy#2. 3 core biopsies will be obtained each time. If a patient undergoes biopsy#1 and refuse biopsy#2 this subject will be replaced. Subjects continue metformin on days of biopsy#2, and take metformin preferably 2 hours prior to the biopsy.

- i. Correlative samples will be collected at baseline, cycle 1 day 1, cycle 1 day 15, Cycle 3 Day 1 and at progression. Analysis will include phenotypic and functional analysis of T and myeloid cell subsets.

- j. Must be within 72 hours of the study drug

*Unless otherwise specified

